## **8.6. Pharmacokinetic Analysis**

Pharmacokinetic parameters will be determined using population PK modeling approach. The sparse PK samples will be pooled with PK data from other clinical studies for population PK analysis. PK profiles will be predicted and subsequently PK parameters will be estimated. Correlations between PK and pharmacodynamic (efficacy or safety) may be explored, including the relationship between drug exposure and viral elimination dynamics, if data permit. The methodology for PK analysis will be documented in a PK Analysis and Reporting Plan outside of this protocol.

## **8.7. Interim Analysis**

One interim analyses will be conducted when 97 resolution events have occurred.

## **8.8. Handling of Missing Data**

### **8.8.1. Imputation**

Severity Symptom Score: Missing values on severity symptom score will not be imputed. Where a patient has died, their status will not be considered missing, but will be imputed with maximum severity score at each timepoint.

Clinical Outcome Scale: Missing values on clinical outcome scale will not be imputed. Where a patient has died, their status will not be considered missing, but will be imputed with maximum clinical outcome scale at each timepoint.

### **8.8.2. Censoring**

Severity Symptom Score: For time to resolution, a patient will be censored if the patient has not had the required timepoint assessment if not due to death. If patient has died or received another antiviral therapy prior to the assessment endpoint, then the patient will be considered as having a moderate or severe COVID-19 symptom for all COVID-19 symptoms and imputed to maximum severity score at the assessment day.

Viral Clearance: For time to viral clearance, a patient will be censored if the patient has not had the required timepoint assessment.

## **8.9. Multiplicity/Multiple Testing**

The primary analysis compares the combined two highest dalcetrapib dose groups against placebo as well as each treatment group individually. For the purposes of inference, if the test of the combined two highest dose groups against placebo is significant at two-sided alpha of 0.05, then the individual doses will be compared against placebo following the Hochberg step-up procedure at two-sided alpha of 0.05.

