### **Determination of Sample Size:**

The purpose of the proof-of-concept study is to identify whether there is sufficient promise of efficacy to justify conducting a Phase 3 study in a larger sample size and to determine efficacious dose to be used in Phase 3. While the entirety of data will be considered at the end of study, the sample size has been chosen to ensure that a positive trend will be present with alpha of 0.2 when considering the two highest doses combined compared to placebo. One-hundred twenty-seven (127) resolution events provides 80% power to demonstrate a positive trend if the average hazard ratio (HR) of the two dalcetrapib groups is 1.4 relative to placebo. Allowing for 20% of patients not resolving, 156 patients (52 per treatment arm) will be enrolled across the two highest dose levels and placebo arms, and an additional 52 will be randomized to 900 mg for a total sample size of 208 patients. One interim analysis will be conducted once 97 resolution events have occurred to allow 73 resolution events to have occurred in the two highest dose levels and placebo arm. At the interim analysis, if the average HR of the two highest dose levels relative to placebo is greater than 1.45, the study will stop due to efficacy and the program will be able to proceed directly to Phase 3. At the interim analysis, if the average HR of the two highest dose levels relative to placebo is between 1.0 and 1.45, the study will continue enrollment until 169 resolution events have occurred. At the interim analysis, if the average HR of the two highest dose levels is less than 1.0, the study will be stopped for lack of efficacy. The final analysis will be performed at an alpha of 0.186. These boundaries were determined by setting the efficacy boundary to follow the power family boundary with  $\rho=2$  and the futility boundary is manually set to HR=1.

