## **8. SAMPLE SIZE AND DATA ANALYSES**

### **8.1. Determination of Sample Size**

The purpose of the proof-of-concept study is to identify whether there is sufficient promise of efficacy to justify conducting a Phase 3 study in a larger sample size and to determine efficacious dose to be used in Phase 3. While the entirety of data will be considered at the end of study, the sample size has been chosen to ensure that a positive trend will be present with alpha of 0.2 when considering the two highest doses combined compared to placebo. One-hundred twenty-seven (127) resolution events provides 80% power to demonstrate a positive trend if the average HR of the two dalctetrapib groups is 1.4 relative to placebo. Allowing for 20% of patients not resolving, 208 patients (52 per treatment arm) will be enrolled. One interim analysis will be conducted once 97 resolution events have occurred to allow 73 resolution events to have occurred in the two highest dose levels and placebo arm. At the interim analysis, if the average HR of the two highest dose levels relative to placebo is greater than 1.45, the study will stop due to efficacy and the program will be able to proceed directly to Phase 3. At the interim analysis, if the average HR of the two highest dose levels relative to placebo is between 1.0 and 1.45, the study will continue enrollment until 169 resolution events have occurred. At the interim analysis, if the average HR of the two highest dose levels is less than 1.0, the study will be stopped for lack of efficacy. The final analysis will be performed at an alpha of 0.186. These boundaries were determined by setting the efficacy boundary to follow the power family boundary with  $\rho=2$  and the futility boundary is manually set to HR=1.

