#### 6.2 Statistical Considerations

Continuous variables will be summarized by the standard descriptive statistics: number of patients (n), mean, standard deviation, median, Q1, Q3, minimum, and maximum, along with confidence interval (CI) for outcome measures when appropriate. Frequency of patient or events and percentages will be summarized for categorical variables, again with CI when appropriate. Time to event variables will be summarized using Kaplan-Meier methods.

All statistical tests will be conducted at a two-sided 0.20 significance level.

Statistical analyses will be performed using SAS Version 9.4 or higher.

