### 6.2.3 Multiplicity/Multiple Testing

The primary analysis compares the combined two highest dalcetrapib dose groups against placebo as well as each treatment group individually. No adjustments will be made for multiple testing.

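### The pooled-dose comparison is tested at two-sided 0.05 in Protocol 8.9 and two-sided 0.20 in SAP 6.2, but the stated 80% power holds only at one-sided 0.20

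*Protocol*

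**What the plan says.** All the statements below concern the same lead comparison, the two highest doses pooled against placebo.

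- **Protocol 8.1** chooses the sample size so that "a positive trend will be present with alpha of 0.2 when considering the two highest doses combined compared to placebo". It adds that "One-hundred twenty-seven (127) resolution events provides 80% power to demonstrate a positive trend" at an average hazard ratio of 1.4. After describing one interim look it says "The final analysis will be performed at an alpha of 0.186". It gives no side for either 0.2 or 0.186. The Synopsis has the same text.
- **Protocol 8.4.1.1** specifies a two-sided stratified log-rank test.
- **Protocol 8.9** proceeds to the individual doses "if the test of the combined two highest dose groups against placebo is significant at two-sided alpha of 0.05", and then applies Hochberg, also at two-sided 0.05.
- **SAP 6.2**: "All statistical tests will be conducted at a two-sided 0.20 significance level".
- **SAP 6.2.3** keeps the pooled comparison and the individual-dose comparisons and says "No adjustments will be made for multiple testing".
- **SAP 6.1** repeats the protocol's 127 events and 80% power. SAP 6.2.1 removes any stopping decision at the interim. SAP section 1 says that the SAP prevails where the two documents differ.

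**The concern.** The threshold in Protocol 8.9 is not the one for which Protocol 8.1 sized the trial, and no section says whether the design alpha is one- or two-sided. This matters in three ways.

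First, an observed pooled hazard ratio in a certain range is a positive result under one document and a negative one under the other. Second, a reader of either document sees 80% power attached to a two-sided test. Third, the trial is meant to support a Phase 3 decision and the choice of dose. Under Protocol 8.9 the dose comparisons sit behind the 0.05 gate. Under the SAP there is no gate and no adjustment.

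**Working it through.** **Inputs**
- 127 events and hazard ratio 1.4 (Protocol 8.1).
- Allocation: "156 patients (52 per treatment arm) will be enrolled across the two highest dose levels and placebo arms" (Synopsis), so 104 active to 52 placebo, or 2:1. The placebo share is 1/3 and the information per event is (1/3)(2/3) = 2/9.
- Interim at 73 events in these three arms, power-family spending with rho = 2, futility at hazard ratio 1 (Protocol 8.1).
- The 127 does refer to three of the four arms: 169 × 0.75 = 126.75 and 97 × 0.75 = 72.75.

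**Step 1: common quantities (Schoenfeld approximation)**
SE of the log hazard ratio = 1/√(127 × 2/9) = 0.188. ln 1.4 = 0.336. Expected Z = 0.336/0.188 = 1.787.

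**Step 2: reproduce the plan's own figures**
The information fraction is 73/127 = 0.575.

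One-sided 0.20:
- Interim spend = 0.20 × 0.575² = 0.066, so z = 1.506.
- SE at 73 events = 1/√(73 × 2/9) = 0.248, so the boundary is exp(1.506 × 0.248) = 1.453 (stated 1.45).
- The final nominal level that uses up the remaining alpha, with non-binding futility, is 0.1862 (stated 0.186).
- Power with the futility stop is 80.0% (stated 80%). It is 82.3% without the futility stop, and 82.8% with a single look.

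Two-sided 0.20, same method:
- Interim boundary 1.58, final one-sided level 0.090, power 67.6% with the futility stop.
- None of the three stated figures is recovered.

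So the design is internally correct as a one-sided 0.20 design. The 0.186 is what remains of 0.20 after the interim look.

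**Step 3: power at the levels the documents use for testing**
Power = Φ(1.787 − z). Critical hazard ratio = exp(0.188z). Events for 80% power = (z + 0.842)² / [(2/9)(ln 1.4)²]. All are single-look figures.

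| Level | z | Power | Critical HR | Events for 80% |
|---|---|---|---|---|
| One-sided 0.20 | 0.842 | 82.8% | 1.17 | 113 |
| Two-sided 0.20 (SAP 6.2) | 1.282 | 69.4% | 1.27 | 180 |
| Two-sided 0.05 (Protocol 8.9) | 1.960 | 43.2% | 1.45 | 312 |

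Spending two-sided 0.05 over the two looks with rho = 2 gives 41.7%, so the interim changes little. If 1:1 allocation were wrongly assumed, two-sided 0.20 would give 73.1% and two-sided 0.05 would give 47.5%. Neither approaches 80%.

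**Step 4: zone where the documents disagree**
A pooled hazard ratio between 1.27 and 1.45 is significant under SAP 6.2 and not under Protocol 8.9. At a true hazard ratio of 1.4 the probability is 69.4% − 43.2% = 26.2%.

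**Step 5: false positives under the SAP**
There are four contrasts (pooled, and each of three doses) against one placebo arm, with equal arms. The correlations are 0.5 between any two doses, 1.5/√(2 × 1.5) = 0.866 between the pool and each dose in it, and 1/√(2 × 1.5) = 0.577 between the pool and 900 mg. In simulation under the global null, with each contrast at two-sided 0.20, at least one is significant in 43.9% of trials in either direction and in 22% in favour of the drug. The pooled test alone has 20% and 10%. With a pooled-first gate at the same level, the familywise figures under the global null would equal those of the pooled test.

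**The case against.** **The SAP prevails.** Its precedence sentence makes two-sided 0.20 without adjustment the operative rule, so the 0.05 gate bites only if Protocol 8.9 is read on its own. This stands: 43% is not the power of the analysis that will be run. It does not remove the conflict between Protocol 8.1 and 8.9, and the operative level has its own shortfall, 69% against the 80% repeated in SAP 6.1. SAP 6.1 does present that figure as the protocol's original calculation, but it restates it beside a two-sided level without comment.

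**The two levels may serve two purposes.** Protocol 8.1 speaks of a trend that would justify Phase 3, with all the data considered, while 8.9 speaks of inference. This reading is possible, but 8.1 also fixes the level of the final analysis at 0.186 for the same comparison, so the text needs clarifying.

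**No adjustment is a legitimate choice in Phase 2a.** This stands. SAP 6.2.3 declares it openly, and restoring the gate and Hochberg step is optional. SAP section 1 also moves emphasis to viral load, which lowers the weight of this endpoint in the decision.

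**Stronger readings that a reader might infer**
- That 0.05, 0.186 and 0.20 are three competing levels. They are not: 0.186 follows from 0.20 by interim spending.
- That the 80% is an arithmetic error. It is not: it reproduces at one-sided 0.20 and was never claimed at 0.05.
- That a false positive for the drug is likely under the SAP. The 44% is below one half and counts both directions. In favour of the drug it is about 22%.

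**Conclusion.** This is an inconsistency, not a calculation error. Protocol 8.9 tests at a level for which Protocol 8.1 did not size the trial. The design works only as a one-sided 0.20 design, which neither document states, while the protocol's log-rank test and the SAP are both two-sided. Power is about 69% at the SAP's operative level and about 43% at Protocol 8.9's level. About one trial in four would be judged differently by the two documents if the true hazard ratio is 1.4.

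These results rest on the Schoenfeld approximation, proportional hazards, 2:1 allocation and 127 events in the three arms. They also assume that the hazard ratio of 1.4 and the event count carry over to the SAP's primary endpoint, which now excludes cough, smell and taste. The SAP did not recalculate either figure for that endpoint, so every power figure here is conditional.

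**What to change.** State one significance level for the pooled comparison, with its side, in both documents. Align Protocol 8.9 and SAP 6.2 to it, and let Protocol 8.1 say how 0.186 follows from 0.2. Replace the bare 80% in Protocol 8.1 and SAP 6.1 with the power that matches the chosen level:

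- one-sided 0.20 with the planned interim: 80%
- one-sided 0.20 with no interim stop, as in SAP 6.2.1: about 83%
- two-sided 0.20: about 69%
- two-sided 0.05: about 43%

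Say that these figures assume a hazard ratio of 1.4 and 127 events for the SAP's endpoint. Keeping the pooled-first gate and Hochberg step is optional. If they are dropped, report the familywise error (about 44% in either direction, about 22% in favour of the drug).

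The cost is wording in two documents, with no change to enrolment or data collection. The printed power may look less favourable.

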## 10. APPENDICES

## Appendix 1 – Adverse Event Definitions

### Definitions

An AE is any untoward medical occurrence associated with the use of a drug in humans, whether or not considered drug related. This includes the following:

- Any clinically significant worsening of a pre-existing condition.
- Note: Emergence of a new pathogen associated with a clinical event during therapy at a site other than the initial site of infection will be considered to be an AE.
- Any recurrence of a pre-existing condition.
- An AE occurring from overdose of a Sponsor study drug whether accidental or intentional (i.e., a dose higher than that prescribed by a health care professional for clinical reasons).
- An AE occurring from abuse of a Sponsor study drug (i.e., use for nonclinical reasons).
- An AE that has been associated with the discontinuation of the use of a Sponsor study drug.

Note: A procedure is not an AE, but the reason for a procedure may be an AE.

A pre-existing condition is a clinical condition (including a condition being treated) that is diagnosed before the patient signs the ICF and that is documented as part of the patient's medical history.

The questions concerning whether the condition existed before the start of the active phase of the study and whether it has increased in severity and/or frequency will be used to determine whether an event is a treatment-emergent AE. An AE is considered to be treatment-emergent if (1) it is not present when the active phase of the study begins and is not a chronic condition that is part of the patient's medical history, or (2) it is present at the start of the active phase of the study or as part of the patient's medical history, but the severity or frequency increases during the active phase. The active phase of the study begins at the time of the first dose of the study drug. The active phase of the study ends at the Follow-up/EOS.

### Reporting of Adverse Events

At each visit the Investigator, or delegate, will determine whether or not any AEs have occurred. Non-leading questions such as "How are you feeling today?" or "Have you had any health concerns since your last visit?" should be used to elicit the patient to report any possible AEs. If any AEs have occurred, they will be recorded in the AE section of the electronic Case Report Form (eCRF) and in the patient's source documents. If known, the diagnosis should be recorded, in preference to listing the individual signs and symptoms.

Adverse event reporting begins from the time of informed consent and ends 30 days after the last dose of study drug.

### **Assessment of Severity**

The Investigator will be asked to provide an assessment of the severity of the AE using the following categories:

- **Mild:** Usually transient and may require only minimal treatment or therapeutic intervention. The event does not generally interfere with usual activities of daily living.
- **Moderate:** Usually alleviated with additional specific therapeutic intervention. The event interferes with usual activities of daily living, causing discomfort but poses no significant or permanent risk of harm to the patient.
- **Severe:** Interrupts usual activities of daily living, significantly affects clinical status, or may require intensive therapeutic intervention.

### **Relationship to Study Treatment**

The Investigator will make a determination of the relationship of the AE to the study drug using a four-category system according to the following guidelines:

- **Not related:** when the AE is definitely caused by the patient's clinical state, or the study procedure/conditions.
- **Unlikely Related:** when the temporal association between the AE and the drug is such that the drug is not likely to have any reasonable association with the AE.
- **Possibly Related:** when the AE follows a reasonable temporal sequence from the time of drug administration but could have been produced by the patient's clinical state or the study procedures/conditions.
- **Related:** when the AE follows a reasonable temporal sequence from administration of the drug, abates upon discontinuation of the drug, follows a known or hypothesized cause-effect relationship, and (if appropriate) reappears when the drug is reintroduced.

### **Action Taken for Adverse Events**

The Investigator or designee will record the action taken for the AE in the eCRF. Actions taken will include:

- **Dose increased:** The medication schedule was modified by addition, either by changing the frequency, strength, or amount.
- **Dose not changed:** The medication schedule was not changed.

- **Dose reduced:** The medication schedule was modified by subtraction, either by changing the frequency, strength, or amount.
- **Drug interrupted:** The medication schedule was modified by temporarily terminating the prescribed regimen of medication.
- **Drug withdrawn:** The medication schedule was modified through termination of the prescribed regimen of medication.
- **Not applicable**
- **Unknown**

### Follow-up of Adverse Events

All (S)AEs that are ongoing at the time of discontinuation, or that develop prior to the final follow-up telephone call, will be followed for 28 days, or until resolution or stabilization.

### Adverse Drug Reactions

All noxious and unintended responses to an investigational medicinal product (i.e., where a causal relationship between an investigational medicinal product and an AE is at least a reasonable possibility) related to any dose should be considered adverse drug reactions.

For marketed medicinal products, a response to a drug which is noxious and unintended and which occurs at doses normally used in man for prophylaxis, diagnosis, or therapy of diseases or for modification of physiological function, is to be considered an adverse drug reaction.

An unexpected adverse drug reaction is defined as an adverse reaction, the nature or severity of which is not consistent with the applicable product information (e.g., Investigator's Brochure for an unapproved IMP).

### Serious Adverse Events

An SAE is any AE occurring at any dose that meets 1 or more of the following criteria:

- Results in death
- Is life-threatening (see below)
- Requires patient hospitalization or prolongation of an existing hospitalization (see below)
- Results in a persistent or significant disability or incapacity (see below)
- Results in a congenital anomaly or birth defect
- Results in an important medical event (see below)

Additionally, important medical events that may not result in death, be life-threatening, or require hospitalization may be considered SAEs when, based on appropriate medical judgment, they may jeopardize the patient and may require medical or surgical intervention to prevent one of the outcomes listed above. Examples of such events include allergic bronchospasm requiring intensive treatment in an emergency room or at home, blood dyscrasias or convulsions that do not require hospitalization, or development of drug dependency or drug abuse.

A ***life-threatening adverse event*** is any AE that places the patient at immediate risk of death from the event as it occurred. A life-threatening event does not include an event that might have caused death had it occurred in a more severe form but that did not create an immediate risk of death as it actually occurred. For example, drug-induced hepatitis that resolved without evidence of hepatic failure would not be considered life-threatening, even though drug-induced hepatitis of a more severe nature can be fatal. Hospitalization is to be considered only as an overnight admission.

***Hospitalization*** or prolongation of a hospitalization is a criterion for considering an AE to be serious. In the absence of an AE, the participating Investigator should not report hospitalization or prolongation of hospitalization. This is the case in the following situations:

- Hospitalization or prolongation of hospitalization is needed for a procedure required by the protocol. Day or night survey visits for biopsy or surgery required by the protocol are not considered serious.
- Hospitalization or prolongation of hospitalization is part of a routine procedure followed by the study center (e.g., stent removal after surgery). This should be recorded in the study file.
- Hospitalization for survey visits or annual physicals fall in the same category.

In addition, a hospitalization planned before the start of the study for a pre-existing condition that has not worsened does not constitute an SAE (e.g., elective hospitalization for a total knee replacement due to a pre-existing condition of osteoarthritis of the knee that has not worsened during the study).

***Disability*** is defined as a substantial disruption in a person's ability to conduct normal life functions (i.e., the AE resulted in a significant, persistent, or permanent change, impairment, damage, or disruption in the patient's bodily function/structure, physical activities, or quality of life).

Medical and scientific judgment should be exercised in deciding whether a case is serious in those situations where important medical events may not be immediately life-threatening or result in death, hospitalization, disability, or incapacity. These include events that may jeopardize the patient or may require medical intervention to prevent one or more outcomes listed in the definition of serious. Such events should usually be considered as serious.

